**NCT05431855**

**Statistical Analysis Plan**

**January 23, 2026**

**Engage project revised statistical analysis plan (Jan. 23, 2026)**

**For CT.gov**

**Aim 1 (Primary outcome):** Explore the impact of engagement strategies implemented via the eWrapper Ranch app on alcohol sensor engagement by comparing the % of sensor wearing over 30 days between those who used eWrapper along with Skyn sensor vs. those who used Skyn sensor without eWrapper.

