5.0 Study Intervention/Investigational Agent

eWrapper-Engagement strategies to facilitate alcohol biosensor wearing: We will conduct a 30-day micro-randomized trial (MRT)--a clinical trial design for developing and optimizing mHealth interventions

PROTOCOL TITLE: A wrist biosensor-based mHealth suite to support alcohol intervention in young people living with HIV

to test which engagement strategy works better, for who, and under what condition among a subset of participants (up to 60). Participants will be micro-randomized in the morning and in the evening, to either a prompt delivering non-contingent small reward (reciprocity); or a prompt containing feedback on self-monitoring progress based on dynamic self-regulation theories (personalized feedback); or no prompt. The eWrapper app will also collect paradata about participants' usage of the app (e.g., how often message notifications were clicked, how often the application was opened). Additionally, information on how long participants wore the Skyn biosensor will be calculated based on downloaded Skyn sensor data from its web portal using an algorithm based on motion and temperature. None of these data will involve any personal identifier. The eWrapper app security has been evaluated by the University of Florida IT risk assessment and deemed acceptable if only used on the study iPhones.

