eWrapper: The eWrapper app was developed by our team and the Florida Center for Interactive Media (FCIM). The app is an animal raising game which includes engagement strategies to promote engagement in terms of wearing the Skyn biosensor. Engagement will be reinforced via a point system and a virtual environment, which starts with a giraffe, but allows the user to unlock new environments, animals, and accessories for their animals. The more the participant wears the Skyn sensor, the more points they will receive as a reward. Also, participants will be micro-randomized in the morning and in the evening, to either a prompt delivering non-contingent small reward (either \$1 cash reward or free points for the game); or a prompt containing feedback on self-monitoring progress based on dynamic self-regulation theories (personalized feedback); or no prompt. During the 30-day period, the number of times the participant will receive these \$1 reciprocity messages will total around 10, accounting for \$10 of their compensation. The eWrapper app will collect paradata as participants use it. Specifically, the following information will be recorded:

- App Usage: when the app is opened and game scenes are loaded

PROTOCOL TITLE: A wrist biosensor-based mHealth suite to support alcohol intervention in young people living with HIV

- **Skyn Data Source Connections:** whenever the eWrapper succeeds or fails to connect to the Skyn wearing time summary database (a Json file).
- **Gameplay Interactions:** whenever the player purchases from the shop, completes the tutorial, interacts with any of the popups or animals, daily reward collections, etc.

Additionally, information on how long participants wore the Skyn biosensor will be calculated based on downloaded Skyn sensor data from its web portal using an algorithm based on motion and temperature. None of these data will involve any personal identifier.

Measures (Short Name)	Required common measure	ENGAGE**	
		T ¹	T ²
Screening		√	
Consent		√	
HIPAA Authorization		√	
Demographics(survey)	√	√	
HIV Viral Load Submission		√	
ART Adherence	√	√	√
Sex Risk	√	√	√
DSM-5 Self-Rated Level 1 Cross-Cutting Symptom Measure—Adult	√	√	√
Alcohol-Smoking-Substance Screening Test (ASSIST)	√	√	√
Timeline Followback	√	√	√
Berger's Scale Revised for Adolescents (HIV Stigma)		√	√
Sexual Sensation Seeking Scale		√	√
Perceived Stress Scale (PSS)		√	√
Pittsburgh Sleep Quality Index (PSQI)		√	√
Usability Acceptability Survey			√

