**Analysis plan:**

We will use our algorithm based on motion and temperature sensor readings from the Skyn biosensor to calculate % of sensor wearing for each participant over 30 days (i.e., total time deemed by the algorithm as wearing divided by maximum possible wearing time which is 24hours\*30days) to see if those who receive eWrapper have higher engagement with the Skyn biosensor.

For CT.gov: upload mean and SD for % wearing time by group

**Aim 2 (Secondary outcome 1):** Explore the feasibility/acceptability of using the Skyn biosensor to monitor drinking among young adults with HIV (YAWH).

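### No SAP aim analyses the micro-randomised prompts, and Aim 1 rests instead on an eWrapper versus no-eWrapper comparison for which no randomisation is described

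*SAP*

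**What the plan says.** Protocol 5.0 describes a 30-day micro-randomised trial "to test which engagement strategy works better, for who, and under what condition among a subset of participants (up to 60"). The unit of randomisation is the decision point within a person: "Participants will be micro-randomized in the morning and in the evening, to either a prompt delivering non-contingent small reward (reciprocity"), or to personalised feedback, or to no prompt. Section 6.0 (eWrapper) repeats this and adds that the reward is either $1 in cash or free game points. Section 1.0 labels the design single group.

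The SAP has three aims. Aim 1 (primary outcome) is to "Explore the impact of engagement strategies implemented via the eWrapper Ranch app on alcohol sensor engagement" by comparing percentage wear over 30 days "between those who used eWrapper along with Skyn sensor vs. those who used Skyn sensor without eWrapper". The outcome is one value per person, "total time deemed by the algorithm as wearing divided by maximum possible wearing time". The stated purpose is "to see if those who receive eWrapper have higher engagement with the Skyn biosensor", and the planned output is to "upload mean and SD for % wearing time by group". Aims 2 and 3 are descriptive ratings of the sensor and of the app. No aim mentions a prompt type, a decision point, an outcome measured after a prompt, or a moderator.

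**The concern.** The only randomisation described within this trial is that of the prompts, and the SAP leaves it unused. The chance triage in Protocol 6.0 assigns people to one of two separate studies before enrolment, so it does not create the eWrapper and no-eWrapper groups.

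Two things are at stake. First, following the SAP as written gives no answer to the question the micro-randomised trial was set up to answer: whether prompts raise wear, and whether reward or feedback does so better. Second, a statement about impact would rest on a between-person comparison open to other explanations. The groups may differ in:

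- **Device.** Section 5.0 says the eWrapper security review accepted the app only on study iPhones. Section 6.0 otherwise sends a study iPhone only to people who do not own an iPhone.
- **Enrolment period and incentives.** The revision history, used here only for chronology, dates the app to version 6.0 (October 2023) and a change in EMA incentives to version 7.0 (April 2024).
- **Payment structure.** Section 6.0 lowers EMA pay by $10 for eWrapper users.
- **Group definition.** Aim 1 groups by those who used the app, while its analysis plan speaks of those who receive it. Grouping by use could select on engagement, which is close to the outcome itself.

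**Working it through.** **1. What is randomised against what is analysed.** Randomisation is within person, twice a day, to three conditions. The Aim 1 outcome is a single 30-day value per person. Everyone using the app passes through all three conditions, so this value averages over them and the between-person comparison cannot separate one from another. It does include the points game, which rewards wearing throughout (Section 6.0) and is not randomised.

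**2. Size of the unused information.**
- Protocol 3.0 and 13.0: 160 × (1 − 0.15) = 136, which reproduces the stated figure.
- Decision points per person: 30 days × 2 = 60.
- Maximum: 60 people × 60 = 3,600.
- With the same 15% attrition: 60 × 0.85 = 51 people, and 51 × 60 = 3,060.

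**3. Randomisation probabilities.** None are stated. Equal thirds with half of the rewards in cash gives 60 × 1/3 × 1/2 = 10 cash messages, which agrees with the roughly ten in Section 6.0. This is not unique, since 60 × 1/4 × 2/3 is also 10. Equal thirds is therefore an assumption.

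**4. Illustrative precision of a prompt analysis.** Assume 51 people, P(any prompt) = 2/3 and a 12-hour wear SD of 20 to 40 percentage points (the documents give no SD).
- Any prompt versus none: half-width = 1.96 × SD × √[1/(3,060 × 2/3 × 1/3)] = 1.96 × SD × √(1/680). This is 1.5 points at SD 20 and 3.0 at SD 40.
- Reciprocity versus feedback, 1,020 decision points each: 1.96 × SD × √(2/1,020). This is 1.7 points at SD 20 and 3.5 at SD 40.
- If clustering inflated the variance fourfold, these would double, to 3.0 to 6.0 points for any prompt versus none.

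**5. How far a group difference unrelated to the app could mislead.** Any such gap passes directly into the difference in means. The SAP plans no test, so the following only shows scale. Take 60 versus 100 people, no app effect, and an assumed 5-point gap from other causes. At an assumed between-person SD of 20, SE = 20 × √(1/60 + 1/100) = 3.27. A two-sided 5% test would then be significant with probability Φ(5/3.27 − 1.96) + Φ(−5/3.27 − 1.96) ≈ 0.33. At SD 10 the figure is 0.87, and at SD 30 it is 0.18. The gap is hypothetical. The documents do not show that one exists.

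**The case against.** The strongest reply is that the SAP suits a pilot. Protocol 2.0 presents eWrapper as a feasibility pilot. The SAP is headed as being for CT.gov, says it explores, and plans only means and SDs. Its phrase about strategies delivered through the app can fairly mean the whole package, game included, in which case bundling is part of the question. A micro-randomised analysis also estimates prompt effects among app users and cannot give the effect of having the app. All of this stands, and it is why the group comparison should be kept. It does not supply an answer to the prompt question in Protocol 5.0.

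A reader might also infer more than the documents support:

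- **That the randomised evidence has been discarded, or that the trial cannot answer the question.** The SAP only fails to specify an analysis. One may exist elsewhere, though none is in these documents.
- **That the prompt analysis is more precise than the SAP's comparison.** A 12-hour prompt effect and a 30-day app effect are different quantities on different scales, the SDs are assumed, and the SAP plans no interval to compare with.
- **That the data are ready.** Section 6.0 lists app usage, sensor connection and gameplay records, and Section 5.0 adds notification clicks. Neither lists the condition assigned at each decision point.
- **That the groups are known to be confounded.** How the subset was chosen is not stated. Study iPhones also go to anyone without an iPhone, and the $10 cut in EMA pay roughly offsets the cash messages.

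**Conclusion.** The omission is real. The protocol states a randomised question, and no SAP aim addresses it. The primary outcome instead rests on a comparison with no described randomisation and two different definitions of the eWrapper group. Up to 3,600 randomised decision points (3,060 with 51 people) have no planned analysis. The half-width of about 1.5 to 3 points for any prompt versus none depends on assumed equal thirds, an assumed SD of 20 to 40 points and no variance inflation. The conclusion does not depend on it, because it follows from setting the two documents side by side.

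Replacing the primary comparison would go too far for a feasibility pilot, since the prompt analysis answers a different question. Adding to it and relabelling it is enough.

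**What to change.** Add to Aim 1 a pre-specified analysis of the proximal effect of the randomised prompt:

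- **Outcome:** percentage wear from each decision point to the next, about 12 hours.
- **Contrasts:** any prompt versus none, and reciprocity versus feedback.
- **Method:** weighted-and-centred least squares or GEE, using the actual randomisation probabilities (which the SAP should state) and participant-clustered robust standard errors.
- **Set:** every randomised decision point, whether or not the prompt was opened.

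Keep eWrapper versus no eWrapper, with these changes. Define the groups by assignment, not use. State how the subset was chosen, and reconcile the limit of 60 with the study procedures paragraph of Section 6.0, which reads as if everyone uses the app. Label the comparison non-randomised and descriptive, and do not attribute the difference to the prompts.

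The sponsor should confirm that the assignment at each decision point, including no prompt, was logged. If it was not, the SAP should say so and explain why the randomised question will go unanswered.

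The cost is SAP wording and programming, with no new participants or procedures. The SAP is already a revision of January 2026, so the added analysis should carry its date and be labelled a late addition.

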2.4	10.05.2022	
Section 6: We have added details about prorating participants' compensation for the EMA assessments if they respond to less than 80% of the assessments. Info about the tutorial videos for the EMA and Skyn apps was included.
 
Section 22: We have added information regarding a video that will accompany the informed consent form
	Yes
3.0	02.01.2023	
We have modified the following protocol sections:
 
Section 1.0: study sample size from 222 to 160
 
Section 3.0: study sample size from 222 to 160, with 15% attrition anticipated
 
Section 6.0: participant incentive schedule to reflect reduced sample size.
 
Section 9.0: Study timeline to reflect new sample size
 
Section 12: Total sample size
 
Section 13: Total sample size
 
We have also updated the consent form to include the sample size change.
	Yes
4.0	06.06.2023	
Section 13: We have modified Section 13 of the protocol to include information related to the use of the BuildClinical platform for social media recruitment. Attached to this modification please find the accompanying materials for IRB review (advertisements, study landing page, pre-screener form, ad copy).
	No
5.0	08.25.2023	
Section 6: We have updated the measures table to include the addition of the Sexual Sensation Seeking Scale
	No
6.0	10.15.2023	
Section 1: Added information on the inclusion of the eWrapper app
 
Section 5: Added the eWrapper app
 
Section 6: Details on the eWrapper app intervention were added. Information regarding how incentives are delivered following completion of baseline and follow up surveys was added. The incentive structure was adjusted to accommodate for the inclusion of the eWrapper app
 
Section 19: Details concerning the security of the eWrapper app were added
	Yes

PROTOCOL TITLE: A wrist biosensor-based mHealth suite to support alcohol intervention in young people living with HIV

		Section 22: Added that an agreement to send back study materials will be included in the consent process	
7.0	04.29.2024	Section 6: We have updated the incentives for EMA assessments to increase retention and to prevent device loss.	Yes

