Once a participant consents and is enrolled, a member of the CEC will contact participants to confirm their HIV and Florida residency status, giving the participants the option to upload documents to the secure REDCap platform or schedule a virtual conference via HIPAA compliant zoom with CEC relationships specialists. These zoom sessions will not be recorded, they will simply be conducted to confirm HIV status for eligibility purposes, if the zoom session is the preference of the participant. If the preference of the participant is to upload proof of HIV status, these documents will not be stored in the DSC participant database; rather, their participant record will be verified by the CEC coordinator and documentation will be removed unless the documentation also serves as the participants viral load as required for study enrollment. Once verification of HIV status, age, and Florida residency is complete, the CEC will confirm the participants method for providing HIV viral load results if not already provided (DBS test kit, release of information, or document upload), and confirm the selection and information in the DSC participant database and notify the AC of any DBS test kits that must be shipped to participants. Only authorized CEC staff and research assistants will directly interact with participants throughout the study.

Engagement and retention efforts: We will maintain regular contact with participants through the contact information provided by them at the time of consent. Reminders will be sent to participants before each assessment.

SHARE Recruitment and Enrollment process:

PROTOCOL TITLE: A wrist biosensor-based mHealth suite to support alcohol intervention in young people living with HIV

Study Procedures: Once enrolled, participants will be asked to wear a wrist alcohol biosensor (BACtrack Skyn) for 30 days, report their alcohol use using daily ecological momentary assessment (EMA), and use the eWrapper app where randomized messages will be delivered to the participant. We will also collect alcohol biomarker (i.e., PEth) at 1-month follow up.

Materials:

1. Online survey including questions on demographic characteristics, alcohol use (including Timeline follow back) and substance use, mental health symptoms, ART adherence, and acceptability & usability of the wrist worn biosensor.
2. An alcohol biomarker Phosphatidylethanol (PEth) will be collected from participants after they complete the 30-day period.

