include reminders to check the battery life of the biosensor and report issues they had with the sensor. Once a survey is completed, the app automatically pushes data into its cloud-based data portal and researchers can access data in real time. Troubleshooting and noncompliance procedures: We will contact participants via phone call if we notice any issues (e.g., missing daily prompt, reported biosensor malfunction) so that these issues can be resolved in time. Drinking data will be obtained via phone call if both daily and self-initiated surveys are missing. Participants will receive \$60 for completing the EMA assessments over the whole 30-day period, if they respond to more than 80% of the EMA assessments. If the participant's response rate is lower than 80%, then the \$60 compensation will be prorated as follows: 60-79% EMA assessment response rate = \$50, 50-59% EMA assessment response rate = \$40, 40-49% EMA assessment response rate = \$30, 20-39% EMA assessment response rate = \$20, 0-20% EMA assessment response rate = \$10. There will be bonus for participants to complete 80% or more EMA assessments. Bonus will increase each week and accumulate to up to \$100 total if they complete 80% or more each week on a continuous basis (Week 1: \$10, Week 2: \$20, Week 3: \$30, Week 4: \$40). If their completion rate falls below 80%, they will not get bonus that week, and the bonus amount resets at \$10 again. Participants will be notified by the study RA during the middle of the 30-day period if their response rate is below the targeted 80%, encouraging them to increase their response rate to be over 80%. For those who also use eWrapper as part of their 30-day trial, they will be expected to receive \$10 from playing the eWrapper game, so their EMA compensation will be reduced by \$10 from the original EMA payment scheme.

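### The SAP's primary comparison of sensor wear with and without eWrapper has no allocation between people, two group definitions and only unadjusted means and SDs, so it cannot separate the app from enrolment period, incentives or phone

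*SAP*

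**What the plan says.** The SAP's Aim 1, labelled the primary outcome, sets out to explore the impact of eWrapper by comparing percentage wear over 30 days "between those who used eWrapper along with Skyn sensor vs. those who used Skyn sensor without eWrapper". The analysis text beneath it states the purpose as "to see if those who receive eWrapper have higher engagement with the Skyn biosensor". The only planned output is "upload mean and SD for % wearing time by group".

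The Protocol's Study Summary labels the study single group. There and in Section 5.0, prompts are micro-randomised twice a day within each app participant, in a subset of up to 60. Section 6.0, under Study Procedures, instead says of enrolled participants generally that they will "use the eWrapper app where randomized messages will be delivered to the participant".

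The revision history dates the app's arrival to version 6.0 (10.15.2023): "Section 1: Added information on the inclusion of the eWrapper app". The same entry adjusts the incentives to fit the app. Version 7.0 (04.29.2024) reads "We have updated the incentives for EMA assessments to increase retention and to prevent device loss". The current Section 6.0 states "There will be bonus for participants to complete 80% or more EMA assessments", and it deducts $100 for devices returned late or damaged.

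On phones, Section 5.0 reports that eWrapper's security was "deemed acceptable if only used on the study iPhones". Section 6.0 otherwise mails a study iPhone only to participants who do not own an iPhone.

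**The concern.** A difference between two groups of people can be credited to the app only if the groups are otherwise comparable, or if the analysis deals with the ways in which they are not. Here nothing makes them comparable. They may differ in when they enrolled, which payment scheme applied, whose phone they carried and, if grouped by use, how engaged they were to begin with. The outcome is itself a measure of engagement, so grouping by app use conditions on something close to the outcome.

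This is the designated primary outcome, intended for registry posting. Two bare means side by side, under an aim worded as impact, invite the reader to take the gap as the app's effect. The planned output gives no difference, interval or adjustment that would show how weak that inference is.

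**Working it through.** **1. The plan's own figures.** 160 × (1 − 0.15) = 136, which agrees with Sections 3.0 and 13.0. Maximum EMA pay without the app is 60 + (10 + 20 + 30 + 40) = $160. With it, 160 − 10 + about 10 paid through the game = about $160. Both agree with the incentive schedule in Section 6.0. No SD, effect size or power is given for the wear comparison.

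**2. Allocation.** The Study Summary, Section 5.0 and the eWrapper paragraph of Section 6.0 randomise prompts within app participants. That contrast concerns which prompt works; it does not concern app against no app. No rule says who enters the subset.

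**3. Period and incentives.** Anyone who finished before version 6.0 could only be in the comparison group. Version 4.0 (06.06.2023) added a recruitment platform, and Section 13.0 explains it as a response to recruitment difficulties, so enrolment was probably under way before October 2023. The documents give no enrolment dates and no counts by group or version. The current pay maximum is about equal in both groups, so any imbalance in total incentives would come from enrolment before as against after the amendments.

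**4. Phone.** If the Section 5.0 condition was followed, every app participant had a study iPhone. In the comparison group only those without an iPhone did, and that number is not given.

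**5. Grouping by use.** Section 15.0 lets participants uninstall the mobile app or leave its features unused, so receipt and use can differ. Assume 60 people issued the app, 100 not, no app effect, the same mean wear in both sets, a share *u* of the 60 using the app, and non-users wearing the sensor *g* points less than users.

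- Non-users dropped: spurious difference = (1 − u)g.
- Non-users counted as without eWrapper: (1 − u)g + 60(1 − u)·u·g / [100 + 60(1 − u)].

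For u = 0.8 and g = 20: 0.2 × 20 = 4.0, and 4.0 + (12 × 16)/112 = 5.7.

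| Use *u* | g = 10: dropped / moved | g = 20: dropped / moved | g = 30: dropped / moved |
|---|---|---|---|
| 70% | 3.0 / 4.1 | 6.0 / 8.1 | 9.0 / 12.2 |
| 80% | 2.0 / 2.9 | 4.0 / 5.7 | 6.0 / 8.6 |
| 90% | 1.0 / 1.5 | 2.0 / 3.0 | 3.0 / 4.5 |

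The range is 1.0 to 12.2 points.

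**6. Precision.** Take an assumed split of 60 × 0.85 = 51 against 100 × 0.85 = 85. The 95% half-width is 1.96 × SD × √(1/51 + 1/85) = 0.347 × SD. For assumed SDs of 15, 20, 25 and 30 points this is 5.2, 6.9, 8.7 and 10.4 points. The spurious differences in step 5 are therefore of the same order as the sampling uncertainty, and the planned output reports neither.

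**The case against.** The strongest reply is that the aim is exploratory. The SAP sets no test, threshold or decision rule, and Section 2.0 frames the eWrapper work as a feasibility pilot. Descriptive means are a fair output for a pilot, and this limits what could go wrong: no formal error rate is breached. It does not cure a primary outcome worded as impact, with groups that are not clearly defined.

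Second, the grouping problem turns on one verb, and the next paragraph of the SAP speaks of those who receive the app. That is right as far as it goes. The firm defect is that the two wordings disagree; the spurious differences above arise only if use governs.

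Third, the conflict over who gets the app is mostly loose drafting. The Study Summary, Section 5.0, the EMA payment text and the incentive schedule all describe a subset. This also stands, but the selection rule is still missing.

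Some stronger readings are tempting, and the documents do not support them:

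- *The comparison group is wholly historical.* A subset of up to 60 leaves room for concurrent participants without the app.
- *The incentive change raised wear.* Version 7.0 concerns EMA pay and device loss, and the bonus rewards EMA completion. A link to wear is plausible, because morning prompts include battery and sensor checks, but it is not shown. Dating the present bonus and deduction to version 7.0 is itself an inference.
- *Newer device versions explain higher wear.* The Background's remark on hardware and software concerns an early device used in the preceding R21 project. No change during this study is recorded.
- *The bias favours the app.* Grouping by use would push that way under the assumptions in step 5. The direction of any period, incentive or phone effect is not established.

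**Conclusion.** The point holds in a limited form. From the text alone: there is no allocation between people and no selection rule, the SAP uses two group definitions, the phone provisions differ, and the only output is unadjusted. By inference: the groups are probably at least partly non-concurrent and may have been paid under different schemes.

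Confounding by period, incentives and phone is of unknown size and direction. The only component that can be sized is grouping by use, at about 1 to 12 points with no true effect. That range rests on assumed group sizes of 60 and 100, use of 70–90% and a wear gap of 10–30 points, and no single value within it should be quoted as the bias. The SDs in the precision check are also assumed. As planned, the comparison can describe wear in two sets of people; it cannot support a statement about the app's impact.

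**What to change.** In SAP Aim 1:

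1. Define the groups by issue of eWrapper at day 0, regardless of later use, and use that definition in both the aim and the analysis text.
2. State how the app subset was chosen, with enrolment dates and counts by group and protocol version. Reconcile Protocol Sections 5.0 and 6.0 on who receives the app.
3. Report the difference in mean percentage wear with a 95% CI, robust or bootstrap because wear is bounded. Adjust for baseline variables already collected (for example age, sex, TLFB drinking, ASSIST and the DSM-5 symptom measure) and, where the groups overlap, for enrolment period or protocol version and for study or own iPhone. If both groups are present among concurrently enrolled participants, add a comparison restricted to them.
4. Where app and period, or app and phone, do not overlap, say that adjustment cannot separate them and report the result as descriptive only. A version covariate does not rescue this: nobody before version 6.0 had the app, so that stratum holds no contrast between app and no app.
5. Replace impact with association.

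The cost is SAP wording, a table of counts and a regression on data that the study collects, assuming that phone issue was recorded. The downside is a wider interval and a weaker claim.
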